PCR polymerase chain reaction

TGF transforming growth factor

AE adverse events

CRF clinical research form

REB research ethics board

IEC independent ethics committee

GCP good clinical practice

TABLE OF CONTENTS

7.0 ASSESSMENT OF EFFICACY 3838**8.0 ASSESSMENT OF SAFETY 3839**

- 8.1 Head MRI 3839

A contrast head MRI will be performed at baseline, 6 months and 12 months for both groups as a safety measure to evaluate any subclinical activity or any paradoxical effect potentially caused by the FMT..... 3839
- 8.2 Adverse events..... 3839
 - 8.2.1 Definition of an Adverse Event 3839
 - 8.2.2 Reporting of an Adverse Event..... 3939
 - 8.2.3 Definition of a Serious Adverse Event 4243

8.4 Reporting of a serious adverse event.....	4243
8.5 Reporting of a pregnancy during the study	4244
9. STATISTICAL ANALYSIS	4344
9.1 Sample Size Selection.....	4344
9.2 Demographics	4344
9.3 Biomarkers	4344
9.4 Safety Analysis	4344
9.5 Criteria for Study Termination.....	4345
9.6 Missing Values	4345
9.7 Evaluable Patients.....	4445
10.1 Protocol Amendments	4445
10.2 Protocol Deviations	4445
11. ETHICAL CONSIDERATIONS	4445
11.1 Independent Ethics Committee (IEC)	4445
11.2 Ethical Conduct of the Study.....	4546
11.3 Patient Information and Consent.....	4546
12. DATA HANDLING AND RECORD KEEPING	4647
12.1 Study Documentation and Record Retention	4647
12.2 Duties of the Investigational Staff.....	4748

1. **Chris H Polman, Stephen C Reingold, Brenda Banwell, Michel Clanet, Jeffrey A Cohen, Massimo Filippi, Kazuo Fujihara, Eva Havrdova, Michael Hutchinson, Ludwig Kappos, Fred D Lublin, Xavier Montalban, Paul O'Connor, Magnhild Sandberg-Wollheim, Alan J Thompson, Emmanuelle Waubant, Brian Weinshenker, and Jerry S Wolinsky. Diagnostic criteria for multiple sclerosis: 2010 Revisions to the McDonald criteria. Ann Neurol. 2011 Feb; 69(2): 292–302. [4849](#)**

CLINICAL STUDY SYNOPSIS

Funding: Chapman Chair in MS Clinical Research - LHSC and LHSF
	
Investigator: [name]

Name of test product: Fecal microbiota
	

Title of the study: Fecal Microbial Transplantation in Relapsing Multiple Sclerosis Patients
	

Principal Investigator and study center:

[name]., FRCP, FACP

St. Joseph's Health Care London

[name]

London Ontario

[name]

Clinical phase: II

Primary objectives:

- To evaluate effects of fecal microbial transplant (FMT) from healthy donors on biological biomarkers as peripheral blood cytokines levels of relapsing multiple sclerosis [RMS] patients from baseline to up to 12 months

Secondary objective:

- To evaluate the safety of FMT in MS patients
- To evaluate tolerability of FMT in MS patients

Trial Design:

The proposed randomized, open label, controlled [treatment as usual control group], crossover study will be conducted in 40 patients (n=20 per group) diagnosed with the relapsing forms of multiple sclerosis according to the McDonald 2010 Criteria¹.

Based on the diagnostic criteria patients will be further screened to confirm eligibility and if eligible then consented.

Patients will be randomized 1:1 into two groups. One group will receive FMT, done by rectal enema administered by a RN, at baseline, month 1, month 2, month 3, month 4, and month 5 (early intervention group). The other group will receive treatment as per standard of care (treatment as usual control group) in the beginning of the study. For the last 6 months they will also receive FMT at month 6, month 7, month 8, month 9, month 10, and month 11 (late intervention group).

Clinical visits for both groups will be performed at baseline, and months 1 to 12 inclusive. During these visits a physical exam with vital signs, including a standardized neurological assessment Expanded Disability Status Scale – EDSS) will be done.

Patient's stools will be collected before each FMT procedure in both groups to evaluate gut microbial composition.

Urine will be collected to evaluate gut permeability at baseline, 6 and 12 months for both groups.

Peripheral blood samples also will be collected to evaluate circulating cytokine levels (IL-1 β , IL-2, IL-4, IL-5, IL-6, IL-9, IL-10, IL-12p70, IL-13, IL- 15, IL-17A, IL-17E/IL-25, IL-17F, IL-21, IL-22, IL-23, IL-27, IL-28A, IL-31, IL-33, GM-CSF, IFN γ , MIP-3 α , TNF α and TNF β) at baseline, months 1 to 12 inclusive for both groups.

Peripheral blood samples will also be collected to evaluate blood DNA bacteria at baseline, and months 1 to 12 inclusive for both groups.

Brain MRI with gadolinium [3T MRI machine at Robarts Research Institute] will be performed at baseline, 6 and 12 months for both groups as a safety biomarker [to rule out paradoxical effects; i.e. significant increase in MS activity as defined by Cutter's rule: 5 or more newly enhancing white matter lesions in the brain compared to the previous scan].

In the event of early termination, a visit will be performed whenever possible, including a final blood sample and all end of treatment assessments that should be completed as soon as possible. All patients with at least 1 week of treatment will be

eligible for analysis.

Number of Patients:

A maximum of 40 patients will be enrolled in intervention part of this study and randomized 1:1 into one of the two groups [20 patients per group] using an internet based randomizer software [<https://www.randomizer.org/>]. We may screen up to an extra 10 patients to compensate for possible drop outs, withdraw consent or those who discontinued for any other reason.

We will also recruit up to 10 healthy volunteers to provide a blood sample [1 tube, 5 ml] to serve as a reference arm for the cytokine analysis. This reference group will be seen only once and will not participate in any other study activities.

Consequently, the total number of participants in this study will be n=50.

Inclusion criteria for patients:

1. Have a confirmed diagnosis of relapsing MS defined by the 2010 Revised McDonald Criteria for the Diagnosis of Multiple Sclerosis¹
2. Have a baseline Expanded Disability Status Scale (EDSS) ≤ 7.0
3. Age equal or older than 18 years of age
4. Be able to attend all clinic appointments without interruption
5. Be proficient in English
6. Be willing and able to give written informed consent
7. Negative blood pregnancy test at screening

Exclusion criteria for patients

1. Not meeting all of the above inclusion criteria
2. Pregnancy [current or planned for the near future] or breastfeeding
3. All qualified patients will not be currently or recently [90 days] treated with immunosuppressive therapy [i.e. chemotherapy] or high dose corticosteroids [i.e. 1g of prednisone or greater or equivalent]. Immune-Modulatory therapies are allowed as per standard of care.
4. Ongoing use of antibiotics
5. Presence of a chronic intestinal disease e.g. celiac, mal-absorption, colonic tumor
6. Concomitant inflammatory diseases
7. Standard of care exclusions for MRI scans as per LHSC standards

Healthy controls Selection:

1. Age equal or older than 18
2. Written informed consent
3. Self reportedly “healthy”, in particular not having a history of any disease or

disorder, or any treatment ever for such [ie lupus, cancer, etc], that in the opinion of the PI could be possibly related to changes in the immune system that would alter the results of a cytokine in blood analysis.

Test product, dose and mode of administration, batch number to be provided by [name] lab at St. Joseph's Health Care, London, ON. For this study, fecal samples from healthy donors will be screened as per Health Canada guidelines. About 50-70g of the fecal sample is blended in 220ml saline in a Stomacher and filtered and transferred to an enema bag for transplantation. From here on this is known as "FMT" or "study medication".

Lot no. XXXXXX

Duration of treatment/study:

FMT rectal enema will be administered as scheduled per group, for up to 6 months.

Criteria for evaluation:

- Circulating cytokines levels (IL-1 β , IL-2, IL-4, IL-5, IL-6, IL-9, IL-10, IL-12p70, IL-13, IL-15, IL-17A, IL-17E/IL-25, IL-17F, IL-21, IL-22, IL-23, IL-27, IL-28A, IL-31, IL-33, GM-CSF, IFN γ , MIP-3 α , TNF α and TNF β).
- Gut microbiome through feces analysis
- Blood DNA bacteria
- Gut permeability through urine analysis
- All adverse events occurring during this study will be recorded. MS clinical functional status will be monitored using EDSS to assess any changes during the treatment period, as well as head MRI as a safety surrogate.

Statistical methods:

Adverse events will be coded using MedDRA dictionary. Incidence of adverse events by the severity, relationship to treatment, and outcome will be provided. Narratives of all serious adverse events and events causing death will be included. Laboratory parameters, vital signs and other safety parameters will be documented with the use of descriptive statistics.

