2. BACKGROUND INFORMATION

Multiple sclerosis (MS) is an autoimmune, inflammatory, demyelinating disease of the central nervous system (CNS) influenced by genetic susceptibility and some environmental factors not yet fully understood³. Relapsing forms of MS (RMS) are generally characterized by clearly defined periods of worsening neurological symptoms [i.e. relapse] followed by full or partial recovery [i.e. with sequelae and residual deficits upon recovery]. Relapsing forms of MS

include relapsing remitting or secondary progressive. In RMS, there is no clinically obvious disease progression during the periods between disease relapses⁴.

Relapses are typically treated with a high dose of glucocorticoids over a short period of time [3-5 days]. Certain immunomodulatory agents, including interferon beta preparations, glatiramer acetate, natalizumab, fingolimod, dimethyl-fumarate, alemtuzumab and teriflunomide, have shown beneficial effects for patients with RMS (decreased relapse rate and a slower accumulation of brain lesions on MRI). However, these treatments may be associated with significant toxicity and limited efficacy over time⁴.

2.1.Pathophysiology of Multiple Sclerosis and gut bacteria

The gut microbiome has recently emerged as a potential contributor to MS pathogenesis^{5,6}. Previously reviewed data from murine model of autoimmune demyelinating disease^{7,8} suggest that gut microbiota can powerfully modulate immune-mediated demyelination. Moreover, studies involving MS patients have shown that their microbial composition is different compared to healthy controls^{9,10,11} and this could be related to disease development and activity¹². Fecal microbial transplantation (FMT) from healthy donors is already used to restore normal fecal flora and treat colitis caused by *Clostridium difficile*. Therefore, we proposed that fecal microbial transplantation from a healthy donor could change the fecal flora composition of RMS patients, have a measurable effect on biomarkers of inflammation and possibly influence clinical or MRI disease activity.

We conducted a review about gut microbiome and MS accepted for publication (Mult Scler 2016 Dec 12. Breaking down the gut microbiome composition in multiple sclerosis).

2.2.Description of Fecal Microbial Transplantation

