6.2.2 Subsequent visits

On all subsequent visits, prior to FMT the following evaluations will be performed:

- Physical examination
- Rapid (urine) pregnancy test for women of childbearing potential;
- Vital signs (including pulse, respiration rate, blood pressure and temperature);
- Concomitant medications;
- EDSS;
- Blood samples will be taken for haematology (including haemoglobin, red blood cell count, white blood cell count, differential and platelets);
- Blood samples will be taken for serum chemistry (including: sodium, potassium, chloride, uric acid, creatinine, blood urea nitrogen, total protein, calcium, albumin, total bilirubin, AST, ALT, alkaline phosphatase, glucose);
- Clean catch, mid-stream urine for urinalysis and micro analysis (including pH, protein, glucose, ketones, nitrites, leukocyte esterase, RBCs, WBCs,);
- Blood sample for blood bacterial DNA
- Blood sample for multiplex cytokine profiling (includes pro-inflammatory (IL-6, IL-15, IL-17, GM-CSF, TNF α) and anti-inflammatory (IL-4, IL-10 and IL-14) cytokines).

After evaluation, the FMT via rectal enema will be performed by a RN in each visit.

At baseline, 6 and 12 months a head MRI will be performed. At these time points urine will be also collected to perform gut permeability analysis.

At any time during the study, if a patient has experienced an adverse event then they may be asked to return to the clinic for an unscheduled visit. Patients with adverse events will be followed to resolution.

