8.0 ASSESSMENT OF SAFETY

8.1 Head MRI

A contrast head MRI will be performed at baseline, 6 months and 12 months for both groups as a safety measure to evaluate any subclinical activity or any paradoxical effect potentially caused by the FMT.

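### The only stated MRI safety criterion counts lesions enhancing on scans six months apart; no cumulative lesion measure is specified, so silent lesions formed during FMT can go uncounted

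*Combined protocol and SAP*

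**What the plan says.** The Synopsis (Trial Design) states that gadolinium brain MRI "will be performed at baseline, 6 and 12 months for both groups as a safety biomarker". It gives one threshold for calling a paradoxical increase in MS activity: "5 or more newly enhancing white matter lesions in the brain compared to the previous scan". Section 6.2.2 and Tables 1 and 2 repeat the three time points and plan no scan in between.

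Section 8.1 puts the purpose more broadly. The scan is there "to evaluate any subclinical activity or any paradoxical effect potentially caused by the FMT". Section 3.2 names EDSS and MRI as the surrogates for paradoxical worsening.

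The early group receives FMT at months 0 to 5 and the late group at months 6 to 11 (Synopsis; Tables 1 and 2). Section 9.4 promises descriptive statistics for safety parameters in general but names no MRI measure. Neither the Synopsis nor sections 3.2, 8.1 or 9.4 mention new or enlarging T2 lesions or any other count that accumulates between scans.

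**The concern.** The criterion counts lesions that are enhancing on the day of the scan. If enhancement is short relative to the six months between scans, a lesion that formed early in the FMT course and has stopped enhancing adds nothing to the count. Section 8.1 asks about any subclinical activity, which is a question about the whole interval.

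What is at stake is how a negative MRI result is read. A statement that no patient met the criterion could be taken as evidence that FMT provoked no silent disease activity, when the criterion had little chance of registering moderate activity. The monthly EDSS and the adverse event review do not close this gap, because they pick up clinical worsening only.

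**Working it through.** The plan gives no figure for the sensitivity of the criterion, so there is none to reproduce. The check has two parts.

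**Schedule (from the Synopsis and Tables 1 and 2).**
- Early group: infusions at months 0, 1, 2, 3, 4, 5; first scan after starting FMT at month 6. Gap from first infusion 6 − 0 = 6 months; from last infusion 6 − 5 = 1 month.
- Late group: infusions at months 6, 7, 8, 9, 10, 11; first scan after starting FMT at month 12. Gaps 12 − 6 = 6 months and 12 − 11 = 1 month.
- Scans strictly between first and last infusion: none in either group.

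**Sensitivity calculation.** Assumptions, none of them in the documents:
- a lesion enhances for a fixed D weeks, with D from 2 to 12;
- lesions arise evenly and independently over the 26 weeks between scans.

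Formulas:
- Share of the interval's new lesions still enhancing at the scan: p = D/26.
- The same share for lesions that arose before the last infusion, taken as weeks 0 to 22: (D − 4)/22, not below 0.
- New lesions needed for an expected 5 enhancing: 5 × 26/D.
- Chance of meeting the rule with N new lesions: P(X ≥ 5), X binomial(N, p).

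| D (weeks) | p | Share, before last infusion | N for expected 5 | P(rule met), N = 10 | P(rule met), N = 20 |
|---|---|---|---|---|---|
| 2 | 7.7% | 0% | 65.0 | 0.05% | 1.6% |
| 4 | 15.4% | 0% | 32.5 | 1.1% | 18% |
| 6 | 23.1% | 9.1% | 21.7 | 5.8% | 50% |
| 8 | 30.8% | 18.2% | 16.25 | 16% | 78% |
| 12 | 46.2% | 36.4% | 10.8 | 53% | 98.5% |

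Example, D = 8 and N = 10: p = 8/26 = 0.308, so 10 × 0.308 = 3.1 lesions are expected to be enhancing, and P(X ≥ 5) = 0.164.

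Letting the duration vary exponentially around the same mean changes little: p becomes 7.7%, 15.4%, 22.8%, 29.6% and 40.9% for D = 2, 4, 6, 8 and 12.

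So 54% to 92% of the interval's new lesions are uncounted across the range. The loss would vanish only if enhancement lasted the full 26 weeks. A count that does not require enhancement on the scan day would in principle capture every new lesion that leaves a T2 trace.

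**The case against.** Four points can be made for the plan.

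1. The size of the problem rests on a quantity that the documents do not give. At the long end, detection is good for heavy activity: with 20 new lesions the rule is met with probability 78% at 8 weeks and 98.5% at 12 weeks. Since the rule is meant to flag a marked increase, it often does so at longer durations. This stands, and it is why the full range is shown. It does not rescue the rule at 2 to 4 weeks, or for 10 lesions at most durations.

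2. Even arrival is a simplification. An effect that builds over six monthly infusions would be caught more often by a scan one month after the last; an effect confined to the first infusions would be caught less often. This also stands; the documents do not say which to expect.

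3. The threshold need not be the whole MRI reading. A reader might infer that the plan excludes all other lesions. It does not: section 8.1 is worded broadly, and section 9.4 allows other safety parameters to be described. The supportable criticism is that no other MRI measure is specified.

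4. MRI is not the only safeguard. EDSS and physical examination are monthly in both groups, adverse events are reviewed at visits after FMT, and unscheduled visits are possible. These limit the risk of missing clinically evident worsening. They do not find silent lesions, which is the task that section 8.1 gives to MRI.

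A reader might also take the remark in section 2 that approved therapies slow lesion accumulation as committing this trial to that measure. It only lists benefits of other treatments and carries no weight here.

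**Conclusion.** The concern holds as a gap in what is measured. The single stated criterion, applied to scans six months apart, leaves part of the activity that section 8.1 asks about uncounted, and the plan specifies no cumulative measure beside it. Under the stated assumptions (enhancement of 2 to 12 weeks, even arrival over 26 weeks), one scan captures about 8% to 46% of new lesions. The direction is the same across that range; the size depends heavily on duration and on the number of lesions.

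A reader might go further and conclude that the MRI safety question will be answered wrongly. The documents do not support that. The risk is conditional on silent lesions forming and ceasing to enhance before the scan, and the plan does not say that meeting or missing the criterion is the only MRI result to be reported. The point is a worthwhile, inexpensive improvement rather than a flaw that undermines the trial.

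**What to change.** Keep the enhancing-lesion rule as written. Add, as a descriptive safety measure, the number of new or enlarging T2 lesions against the previous scan, read from the month-6 and month-12 images already planned. Report it by group, with the between-group difference at month 6, which is the only post-baseline scan at which a concurrent randomized group has not yet had its FMT course. State it in section 8.1 and list it in section 9.4.

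The gain assumes that most new lesions leave a lasting T2 trace, which the documents do not address. The added count has no threshold, so the existing criterion could still be reported as unmet; the count would stand beside that statement and show whether lesions had accumulated. No extra scan or visit is needed. The cost is slightly longer MRI reading.

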3.2 Secondary outcomes

We are also aiming to evaluate if FMT can possibly alter gut permeability through urinalysis and peripheral blood DNA bacteria. We also aim to evaluate treatment safety using the Expanded Disability Status Scale (EDSS) and MRI as surrogates for any paradoxical worsening in MS disease activity. We are monitoring adverse events to assess tolerability.

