6.3 Sample Size analysis

It was assumed that the acceptable Type I error will be 0.05 and power will be 0.8. Moderate effect size effect is expected. This is a study of a kind that has never been done before in this population. From similar studies in other populations or other interventions on a similar population, a 40% change in cytokine levels (ie TGFbeta1) analysis is expected, as reported on other cytokine study with no pharmacological intervention, such as vitamin D supplementation⁷³.

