9. STATISTICAL ANALYSIS

9.1 Sample Size Selection

This is an exploratory proof of concept immunological study. As such the number of patients in each treatment group was arbitrarily chosen in lieu of a convenience sampling for this type of study.

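### The only MRI measure defined for paradoxical MS activity is a per-patient cut at 5 new enhancing lesions; with 20 per group it is too coarse a group summary to exclude an increase, and the lesion counts should be reported and compared as well

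*Combined protocol and SAP*

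**What the plan says.** The synopsis (Trial Design) schedules gadolinium MRI at baseline, 6 and 12 months in both groups, as a safety biomarker meant to exclude paradoxical effects. It defines a significant increase in MS activity, by a named rule, as "5 or more newly enhancing white matter lesions in the brain compared to the previous scan".

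Two other sections describe a wider purpose. Section 8.1 has the scans done "as a safety measure to evaluate any subclinical activity or any paradoxical effect potentially caused by the FMT". Section 3.2 treats EDSS and "MRI as surrogates for any paradoxical worsening in MS disease activity". Neither names a lesion count, a rate or any other MRI variable.

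On analysis, section 9.4 (repeated in the synopsis) promises descriptive statistics for laboratory values, vital signs and other safety parameters. MRI is not named. Section 9.3 specifies a mixed-design ANOVA for biomarkers and does not name MRI either.

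On size, "Patients will be randomized 1:1 into two groups" of 20. Section 6.3 gives an alpha and a power, but for a cytokine change. Section 9.1 says: "As such the number of patients in each treatment group was arbitrarily chosen".

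**The concern.** The stated purpose and the stated measure do not match. A patient with 1 to 4 new enhancing lesions at month 6 has subclinical activity of the kind section 8.1 wants evaluated, yet is negative on the only criterion the plan defines. Nothing commits the sponsor to tabulate or compare the counts, although the lesions must be counted to apply the rule.

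What is at stake is how the safety result can be read. If the report says that no patient met the 5-lesion criterion, the synopsis wording invites the conclusion that a paradoxical effect has been excluded. Month 6 is also the only randomised MRI contrast of treated v untreated patients, because the late group receives FMT from then on. In an open-label study, leaving the MRI summary unspecified also allows it to be chosen after the data are seen.

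**Working it through.** **The plan's own figure.** There is none to reproduce. The documents give no expected lesion rate, dispersion, detectable difference or power for MRI.

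**Inputs from the documents.** 20 per group; cut at 5 or more newly enhancing lesions since the previous scan; randomised contrast at month 6. I take the late group's month-6 scan to precede its first FMT, which is scheduled for the same study month. All 40 patients are assumed scanned, which is the best case.

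**Step 1: results that need no lesion-rate assumption.**
- Upper limit after 0/20: solve (1 - p)^20 = 0.05, so p = 1 - 0.05^(1/20) = 0.139. The one-sided 95% limit is 13.9%.
- Two-sided Fisher test, 0/20 v x/20: p = 2 × C(20,x)/C(40,x).
  - x = 4: 2 × 4,845/91,390 = 0.106.
  - x = 5: 2 × 15,504/658,008 = 0.047.

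So a quarter of one arm must cross the cut, with nobody crossing it in the other, before the arms differ at 0.05.

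**Step 2: results under assumed lesion rates.** Counts per scan are taken as negative binomial with mean m and dispersion k (variance m + m²/k). Low means are plausible because entry allows any disease duration, secondary progressive MS and ongoing immunomodulatory therapy, and requires no MRI activity. This remains an assumption.

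Centre case, m = 0.5, k = 0.5, threefold rise to m = 1.5:
- P(0 lesions) = (k/(k+m))^k. Untreated: (0.5/1.0)^0.5 = 0.707. Treated: (0.5/2.0)^0.5 = 0.500.
- P(5 or more), from the negative binomial tail: 1.0% untreated, 9.8% treated.
- P(1 to 4): untreated 1 - 0.707 - 0.010 = 28%; treated 1 - 0.500 - 0.098 = 40%.

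The cut therefore treats the 40% with 1 to 4 lesions the same as the 50% with none.

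Power at k = 0.5, 20 v 20, two-sided 0.05. The cut uses exact Fisher power. The rank test and a negative binomial likelihood-ratio test calibrated to 5% were simulated (800 trials per cell, standard error up to about 1.8 points).

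| Untreated mean | Rise | Share at 5 or more, untreated → treated | Cut | Rank test | Negative binomial |
|---|---|---|---|---|---|
| 0.3 | 3x | 0.2% → 4.0% | 0.1% | 30% | 43% |
| 0.3 | 4x | 0.2% → 6.9% | 1% | 48% | 63% |
| 0.5 | 3x | 1.0% → 9.8% | 3% | 35% | 43% |
| 0.5 | 4x | 1.0% → 14.5% | 13% | 53% | 62% |
| 1.0 | 3x | 4.9% → 22.6% | 24% | 37% | 57% |
| 1.0 | 4x | 4.9% → 29.0% | 42% | 59% | 79% |

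Over means 0.3-1.0 and k 0.3-1.0, the cut v the rank test gave about 0-35% v 21-64% for a threefold rise, and about 0-63% v 31-83% for a fourfold rise. Counts won in every setting. In the centre case, 80% power for a threefold rise with the cut would need about 103 per group (normal approximation).

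**Step 3: limits of this comparison.**
- Fisher's actual null rejection in these settings is 0-0.4%, against 4-5% for the rank test. Part of the gap is the conservatism of the exact test, not the cut itself.
- With a high mean and little overdispersion (m = 2, k = 1) the cut reaches 54% (3x) and 76% (4x), still below the counts at 83% and 97%.
- With strong overdispersion (k = 0.25) even the negative binomial test reaches only 26-37% (3x) and 38-50% (4x).

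**The case against.** The strongest reply is that no planned analysis is damaged. Section 9.4 plans description only, so the Fisher test above was supplied for illustration. The rule is worded as a within-patient change and reads as an individual flag from a named source, which cannot be checked here. Nothing bars reporting lower counts under 9.4. EDSS is assessed at every visit and adverse events are recorded, so MRI is not the only safeguard. The study calls itself exploratory, with an arbitrary sample size. All of this stands, and it limits the point to how the MRI safety result is summarised and read. It does not remove the point: a descriptive table of the proportion at 5 or more loses the same information, and no text commits to anything more. Someone might argue that 9.3 covers MRI because the synopsis calls it a safety biomarker, but no MRI variable is specified there.

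Some stronger readings are tempting and are not supported:
- *A planned MRI test is underpowered.* No such test is planned.
- *The plan classes 1 to 4 new lesions as no effect, or fixes how a null result will be read.* No section says so. Excluding paradoxical effects is the scans' stated purpose, not a decision rule.
- *Zero or one patient at the cut is the likely result whether or not FMT is harmful.* In the centre case, the chance of 0 or 1 among 20 treated patients is 40% after a threefold rise and 19% after a fourfold rise. At mean 1.0 it is at most about 6%. The statement is reliable only near mean 0.3.
- *The counts would show a threefold rise.* They would usually miss it too.

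**Conclusion.** The concern holds in a limited form. The only defined MRI measure is narrower than the purpose given in 8.1 and 3.2. With 20 per arm, the absence of patients meeting it cannot exclude a group increase: 0/20 is compatible with a true rate of up to 13.9%. That figure and the 5/20 requirement rest on the sample size alone.

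The size of the gain from using counts rests on assumed lesion rates and dispersion. Over the range tried, the counts were always more sensitive, by a large margin at low lesion rates, but remained poorly powered for a threefold rise in most settings. This is a cheap improvement to the safety summary, not an error in a planned comparison. Whether 5 is the right threshold for acting on an individual patient is a clinical question and is not judged here.

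**What to change.** Leave the 5-lesion rule as the individual-patient flag. Add to section 9.4:
- Newly enhancing lesions per patient at month 6 will be summarised by group (distribution, mean, proportion with any) and compared, early v late.
- The comparison will be a rate ratio with 95% CI from a negative binomial model with the baseline enhancing count as covariate, or a rank test if the model is unstable. With 20 per arm the uncalibrated likelihood-ratio test rejected 4.5-7.6% under the null in the settings simulated, so a permutation p-value is a sensible safeguard.
- The proportion at 5 or more will be reported alongside, with an exact interval.
- The absence of patients meeting the 5-lesion rule will not by itself be taken to exclude a group increase.

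Fix this before any month-6 MRI data are compared by group. The cost is a paragraph of text and one extra exploratory analysis. No new scans or readings are needed, because the lesions must already be counted. The drawback is a wide interval that will look less reassuring than a statement that no patient met the criterion.
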